Structural MRI. Whole brain axial gradient-echo MPRAGE T1-weighted images will be acquired for 31P and fMRI localization (TE/TR 3.57/2730ms, flip angle = 7 degrees, slice thickness=1mm, Gap=0 (contiguous slices), FOV=25.6cm, 256×256 matrix size & 2.0×2.0mm resolution; 5 minutes duration). 2D/3D FLAIR imaging will be acquired, time allowing within the 1.5 hour scan, to assess white matter hyper-intensity load (~6 minutes duration). High resolution hippocampal imaging will be performed, time allowing within the 1.5 hour scan, to allow localization of functional connectivity analysis seeds in the hippocampus and frontal regions and assessment of possible structural improvements related to intervention (~5 minutes duration). 3D PASL sequence (TE/TR=10.5/4885ms, PLDelay=2000ms, 1.9x1.9x4mm resolution, FOV = 240 x 240 x 160mm) will enable quantification of changes in cerebral perfusion related to intervention. Data will be analyzed using AFNI to compute regional and whole brain estimates of resting cerebral perfusion pre and post intervention.

Phosphorous MRS. A 31P-MRS pulse-acquired sequence will be acquired from two 6-cm³ voxels centered in prefrontal cortex and temporal cortex to assess region-specific change in phosphorous MRS-based markers of ATP function and brain health. Parameters: TE 0.1ms; TR 4500ms; Spectral resolution 2.4 Hz/point; Spectral bandwidth 3000 Hz; 7 minutes duration). Analyses: Spectra will be analyzed using Tarquin to give concentrations for the following phosphorous metabolites: nucleoside di- and tri-phosphate (gamma, alpha, beta-NTP), phosphoethanolamine (PEtn), phosphocholine (PCho), glycerophosphoethanolamine (GPEtn), glycerophosphocholine (GPCho), 2,3 diphospho-glyceride (DPG), inorganic-phosphate (Pi), membrane-bound phospholipid (MP), and phosphocreatine (PCr). The signal amplitudes of brain tissue and CSF will be derived (corrected for T2 decay), with brain water signal used to correct for partial CSF volume. MRS Quality Assurance: The concentration measures for the metabolites will be accepted with Cramer-Rao lower bounds (%SD) of less than 20%, a reliable estimate for a particular metabolite for group comparisons. Scans resulting in spectra that do not meet quality criteria will be repeated. Line width and signal-to-noise resonance ratios are plotted over time (brain, phantom) to monitor spectral quality; inter- and intra-subject variability assessed by correlation and Bland and Altman plots.

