7.3. Statistical Analyses

Data for each group (Cognitively Normal, MCI, Parkinson) will be analyzed separately. However the same analytic approach will be taken for each, as described below. Some analyses will be truncated for the MCI groups due to the smaller sample size.

Aim 1: Aim1 will test the hypothesis that individuals in the active stimulation group will show improved cognitive function compared to the sham group. Separate mixed model ANOVAs (2 [Group: Active Stimulation, Sham stimulation] x 2 [Occasion: Pre-testing, Post-testing]) will be conducted using the executive and Memory outcome variables. When significant, appropriate post-hoc analyses will be conducted. Additional analytic techniques will involve 'change score' analyses, as well as analyses examining predictors of changes (i.e., age, education, gender).

Aim 2: Aim 2 will test the hypothesis that individuals in the active stimulation group will show improved emotion/psychological function compared to the sham group. Separate mixed model ANOVAs (2 [Group: Active Stimulation, Sham stimulation] x 2 [Occasion: Pre-testing, Post-testing]) will be conducted using the mood outcome variables (mood modules NIH Toolbox, STAI, POMS, BDI-II). When significant, appropriate post-hoc analyses will be conducted. Additional analytic techniques will involve 'change score' analyses, as well as analyses examining predictors of changes (i.e., age, education, gender).

Aim 3: This neuroimaging aim is exploratory and will test the hypothesis NIR intervention will produce pre-post increases in frontal and temporal brain markers of MRS ATP function and pre-post increases in connectivity in frontal and medial temporal lobe mediated resting state brain networks (resting state fMRI). Although this aim will require extensive data reduction, the overall data analytic plan is similar to that of Aims 1 and 2.

Aim 4: This is aim is specific to Parkinson disease and will test the hypothesis that active NIR stimulation will result in greater pre-post intervention improvement in motor parameters (UPDRS, fine motor speed, gait, balance) than sham. Separate mixed model ANOVA's will be conducted similar to those described in Aims 1 and 2.

Finally, we plan to examine whether various 'factors' might potentially be moderators or mediators to intervention success. WE plan to examine age, education, gender, health comorbidities, processing speed and mood.

8. Methodological Limitations

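### The 20% relative Cramer-Rao cut in section 6.8 filters on the Aim 3 ATP outcome and can attenuate a true increase, by an amount that depends on a noise level the documents do not give

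*Protocol*

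**What the plan says.** Protocol section 6.8 (Phosphorous MRS) takes spectra from "two 6-cm³ voxels centered in prefrontal cortex and temporal cortex". It then states: "Spectra will be analyzed using Tarquin to give concentrations for the following phosphorous metabolites", a list that includes the gamma, alpha and beta NTP signals. The quality rule is "The concentration measures for the metabolites will be accepted with Cramer-Rao lower bounds (%SD) of less than 20" per cent, which the same sentence describes as "a reliable estimate for a particular metabolite for group comparisons". On failures it adds: "Scans resulting in spectra that do not meet quality criteria will be repeated". Line width and signal-to-noise are plotted over time, but no limit is set for either.

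Section 7.3 states the Aim 3 hypothesis: "NIR intervention will produce pre-post increases in frontal and temporal brain markers of MRS ATP function". On the analysis it says that "the overall data analytic plan is similar to that of Aims 1 and 2", that is, a 2 x 2 mixed ANOVA with change scores as an addition. Section 6.8 labels the imaging exploratory and a source of pilot data. The SAP names only cognitive and emotion outcomes.

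Neither document gives an absolute bound, a signal-to-noise ratio or an expected %SD for ATP. Neither says how many repeats are allowed, or what becomes of a value that still fails.

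**The concern.** A quality filter should depend on how good the measurement is, not on the value measured. A relative bound depends on both, because the estimate is its denominator. Two scans of identical spectral quality can be treated differently only because one person's ATP is lower. Here the filtered quantity is itself the outcome, and the hypothesis is that treatment raises it. If the hypothesis is true, acceptance depends on arm and visit: active post-treatment values clear the cut more often than baseline or sham values.

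What is at stake is the size of the ATP effect that this imaging subset is meant to estimate for later trials.

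**Working it through.** The 20% cut is a rule, not a derived figure, and the plan gives no sample size or effect for MRS, so there is no plan figure to reproduce.

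**Step 1, the rule.** Let C be the person's estimated concentration and s its absolute bound. %SD is not defined in the protocol; in the usual sense it is s/C. Then s/C < 0.20 is the same as C > 5s.

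**Step 2, assumed inputs (none is in the documents).** Baseline and sham mean 1; true active increase e = 0.10 at post; between-person SD b = 0.15 or 0.25; pre-post correlation of true values 0.6; bound s between 0.05 and 0.18, the same for every scan; a participant is analysed only if both scans pass; no repeats.

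**Step 3, formula.** An estimate has SD σ = √(b² + s²), and pre and post estimates have correlation R = 0.6b²/σ². Put h = (5s − 1)/σ and k = (5s − 1 − e)/σ. Let φ be the standard normal density, Φ̄ its upper tail, q = √(1 − R²), and P the probability that both active scans pass. For a truncated bivariate normal,

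mean kept change, active = e + σ(1 − R)(A − B)/P,

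where A = φ(k)Φ̄((h − Rk)/q) and B = φ(h)Φ̄((k − Rh)/q).

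In the sham arm k = h, so A = B and the mean kept change is 0. The active expression is therefore the arm difference. The same identity gives exactly 0 when e = 0, so there is no bias under the null.

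**Step 4, one case in full (s = 0.15, b = 0.15).** 5s = 0.75; σ = √(0.0225 + 0.0225) = 0.2121; R = 0.6 × 0.0225/0.045 = 0.30; h = −0.25/0.2121 = −1.179; k = −0.35/0.2121 = −1.650. A single post scan passes with probability 88.1% in sham and 95.1% in active. A = 0.0781, B = 0.1819, P = 0.8451. Difference = 0.10 + 0.2121 × 0.70 × (0.0781 − 0.1819)/0.8451 = 0.10 − 0.018 = 0.082.

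**Step 5, the range (true difference 0.100).**

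| Bound, % of mean | b = 0.15: kept sham / active | Difference | b = 0.25: kept sham / active | Difference |
|---|---|---|---|---|
| 5 | 100% / 100% | 0.100 | 99.7% / 99.8% | 0.100 |
| 8 | 100% / 100% | 0.100 | 98.0% / 98.6% | 0.098 |
| 10 | 99.5% / 99.7% | 0.099 | 94.3% / 95.9% | 0.095 |
| 12 | 96.5% / 97.7% | 0.096 | 87.2% / 90.2% | 0.089 |
| 15 | 79.0% / 84.5% | 0.082 | 68.7% / 74.1% | 0.078 |
| 18 | 47.6% / 56.0% | 0.062 | 45.3% / 51.7% | 0.064 |

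**Step 6, repeats (simulation, b = 0.15).** One repeat of each failing scan at a 15% bound lifts retention from 79.0% / 84.5% to 92.3% / 94.9%, but the difference stays at 0.082. At a 20% bound it moves from 0.051 to 0.047.

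**Step 7, noise that varies between scans (simulation, log-SD 0.3, b = 0.15, no repeats).** The raw difference is 0.099 at a typical bound of 8%, 0.090 at 15% and 0.084 at 20%. Cohen's d, unfiltered against kept, is 0.389 against 0.396 at 15%, and 0.308 against 0.317 at 20%. With constant noise d does fall: 0.397 to 0.365 at 15%, and 0.319 to 0.233 at 20%.

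**Step 8, the alternative.** Accept if s divided by a fixed reference concentration is below 0.20. The person's estimate no longer enters, so acceptance cannot depend on the effect. In the varying-noise simulation the difference is 0.099 to 0.101 at every bound from 5% to 25%. At 15%, retention is 75.0% in both arms and d rises from 0.385 unfiltered to 0.418.

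**The case against.** The strongest reply is that nothing in the documents places ATP near the cut. If its bound is 10% of the mean or less, almost every value passes and the loss is at most about 5% of the effect (0.095 against 0.100). The rule also has a purpose that a constant-noise model leaves out: it removes poor spectra. When noise varies between scans, d hardly changes compared with no filter. The aim is exploratory and confined to an imaging subset. All of this stands, and it limits the size and priority of the point. It does not answer the mechanism, and a cut on absolute error keeps the benefit without the selection.

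Four stronger readings are tempting and are not supported.

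- A reader might infer that the rule does shrink the ATP effect. That needs both a true increase and bounds near the cut; the documents establish neither.
- A reader might take the loss to be larger, a 10% increase showing as about 5 to 7.5%. That compares post-treatment scans alone at bounds of 15 to 18%. Aim 3 is a pre-post analysis, in which baseline filtering is equal in the two arms and partly offsets the loss.
- A reader might infer that repeating scans makes the selection worse. One repeat left the difference unchanged at a 15% bound and lowered it slightly at 20%. Section 6.8 also ties repeats to spectra that fail quality criteria and does not say that one low metabolite value triggers a rescan.
- A reader might fear false positives. With no true effect the bias is zero.

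**Conclusion.** The point holds as a conditional one. With %SD read as bound over estimate, the rule selects on the Aim 3 outcome and pulls a true ATP increase towards zero on the raw scale; repeats restore participants but do not remove the attenuation.

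For a true 10% increase, the change-score difference is about 9.5 to 10% if the bound is 5 to 10% of the mean, 8.9 to 9.6% at 12%, and 6.2 to 8.2% at 15 to 18%. These figures rest on the assumed between-person SD, correlation, constant noise and both-scans requirement above. If noise varies between scans, the raw difference still shrinks but d changes little.

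This is a minor, cheap improvement to an exploratory imaging aim. It does not touch the cognitive or mood outcomes.

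**What to change.** In section 6.8:

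1. Replace the %SD cut with one that does not use the individual's estimate, for example an absolute Cramer-Rao bound below 20% of a fixed reference concentration for each metabolite. The pooled baseline mean would serve, set blind to arm and computed before any filtering.
2. Base rescans on line width and signal-to-noise only. Limits for both must be written, because at present they are only plotted. State how many repeats are allowed and what happens to a value that still fails.
3. Report rejections by metabolite, arm and visit, and show the Aim 3 results with and without the %SD cut.

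No extra scanning is needed. The SAP is written in the past tense; if acquisition is complete, items 1 and 3 can still be done from stored spectra wherever failing ones were kept. The costs are that the limits and reference values have to be specified, and that some low concentrations with high relative error stay in the analysis.

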7.1. Outcome Measures

Aim 1 examines executive function and memory using sensitive cognitive measures.

- Co-Primary Executive Outcome: Changes in pre-post treatment scores on: a) executive composite and domain scores derived from the NIH Examiner and b) the Stroop interference score.

- Co-Primary Memory Outcomes: Changes in pre-post treatment scores on memory measures including a) delayed recall scores and composite from the Arena and b) delayed recall score from the AVLT. Secondary outcomes include other executive and memory measures as well as potential mediator and moderator variables such as processing speed.

Aim 2 examines well-being and mood variables.

- Co-Primary outcome: Changes in pre-post treatment scores on the Negative Affect and Psychological Wellbeing scales from the NIH Toolbox emotion module.
- Secondary outcomes: Changes in pre-post treatment scores on traditional mood measures including the 1) State-Trait Anxiety Inventory (STAI; Spielberg, 1989), the 2) Profile of Mood States (POMS; Curan et al., 1995), 3) Beck Depression Inventory-II (BDI-II; Beck et al., 1996), and 4) Apathy Scale.

Aim 3 is an exploratory neuroimaging aim that will examine changes in resting state functional connectivity as a function of group status (NIR stimulation vs Control). We are particularly interested in potential changes in MRS spectroscopy, particularly those elements associated with phosphorous ATP

Aim 4 pertains to motor variables that are being examined in patients with Parkinson disease

- Outcomes include: Changes in pre-post intervention scores on the Grooved Pegboard Task, scores on the UPDRS rating scale, and gait and balance measures on the GAIT-Rite scale.

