6.6.1 Executive Measures [NIH Examiner, Stroop]

The executive measures include the NIH Examiner, a computerized battery consisting of 9 individuals subtasks described below, and a measures of cognitive inhibition (Stroop task). During post-intervention, an executive measure given as part of screening (Trail Making Test) will be repeated.

6.6.1a Description of the NIH Examiner: The National Institutes of Health Executive abilities: Methods for Neurobehavioral Evaluation and Research (Kramer et al., 2012). The NIH Examiner is a computer based battery that involves nine tasks of frontal-executive function and takes around 45 minutes to complete. Funding for development of the NIH Examiner was provided by NINDS in 2005 to develop sensitive, domain-specific tasks of fronto-executive function. The NIH Examiner consists of 9 individual tasks that can be combined into three domain specific scores: *Cognitive Control, Working Memory, and Fluency*. An overall *Executive Composite* score can also be computed (Kramer et al., 2014). In the current study, the **dependent variable for the primary aim will be the “executive composite”**

score calculated from the tasks within the NIH Examiner. Described below are each of the 9 tasks of the battery.

1. *Dot Counting (working memory)*: Participants look at a mixed array of green circles, blue circles, and blue squares. They are asked to count all of the blue circles and remember the final total, before counting the blue circles on new displays. The number of new displays increases from two to seven over a total of six experimental trials. The dependent variable is total correct score over trials 1-6, which contributes to the Executive Composite and the Working Memory factor scores.

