5. *Anti-saccades (inhibition)*: In this task, participants are asked to watch a moving dot on the computer screen and move their eyes upon presentation of a laterally presented stimulus. Some trials involve moving eyes in the direction of the presented stimulus (prosaccade, 10 trials), and some involve moving eyes in the opposite direction (anti-saccade, 40 trials). The dependent variable is the total number of correct anti-saccade trials, which contributes to the Executive Composite and Cognitive Control factor scores.
6. *Set Shifting (set-shifting)*: Participants are required to match a stimulus on the top of the screen to one of two stimuli located in the lower corners of the screen. Stimuli are matched either based on color or shape depending on the cue. There are three tasks: Task A involves matching stimuli based on shape (homogenous; 20 trials), Task B involves matching stimuli based on color (homogenous; 20 trials), and Task C alternates between matching stimuli based on shape and color (heterogeneous; 64 trials; 32 shape, 32 color). Both reaction time score and accuracy scores are calculated across all blocks. These two scores are summed to create the dependent variable, a total set shifting score. This total set shifting score is used to calculate the Executive Composite and the Cognitive Control factor scores.
7. *Phonemic Fluency (fluency)*: In this task, participants are asked to generate as many words that begin with a particular letter of the alphabet. The task is timed for one minute and participants are given two different letters (F and L) for which they must generate words. The dependent variables are the total number of correct words generated on F and L trials, which contribute to the Executive Composite and Fluency Factor scores.
8. *Category Fluency (fluency)*: This task is similar to “phonemic fluency”. However, participants are

asked to generate as many words possible that belong to a particular category. This task is timed for one minute and participants are given two categories (animals and vegetables) for which they must name items. The dependent variables are the total number of correct words generated on animal and vegetable trials, which contribute to the Executive Composite and Fluency Factor scores.

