Hidden target condition. After subjects have learned the task, they will participate in 8 invisible-target acquisition trials. In these trials the target is not visible from afar and is discoverable only when the joystick or direct pad icon is hovered over the target. A trial begins with a fixed tour of a new room, where each wall is shown for approximately 2 seconds during two sweeps of the room. Participants are instructed that the hidden target will be in the same place on each trial and that their task is to find it as soon as possible. Participants are typically given 120 seconds to find the target. During the first 2 trials, the examiner takes over after 120 seconds and assists the participant finding the target. No assistance is given after the initial two trials. If the target has not been located after 120 seconds in the later trials, the trial ends and a 10-second inter-trial interval (ITI) ensues, and the next trial begins. If the subject acquires the target on any trial, it becomes visible and a pleasant auditory signal additionally alerts them to target acquisition. They are allowed to stay on the acquired target for 15 seconds and are encouraged to rotate-in-place to survey the environment. After this, the 10-second ITI ensues and the next trial begins at a different compass point. A final spatial memory probe occurs following the 8th trial. On this final trial, the invisible target is removed unbeknownst to the participant. This means that target acquisition is not possible, but search behavior is evaluated with regard to the percent of the 120-second trial that is spent in the quadrant containing the target. On each acquisition trial, path length, time to acquire the target, and target acquisition (yes-no) are recorded. On the probe trial, path length and percent of time spent in each quadrant of the Arena is recorded. A composite score, consisting of mean z-scores on path length, time to acquire target, and percent of time spent in the proximal quadrant on the probe trial, will also be calculated. **The dependent variable will be this navigational performance composite.**

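### Aim 1 primary outcomes differ between protocol sections 5, 6.6 and 7.1, one listed Arena score does not come from the task as described, and no alpha or success rule is set

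*Protocol*

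**What the plan says.** **Executive function.** Section 6.6.1a states that the "dependent variable for the primary aim will be the" Examiner executive composite. It also explains that the battery has "9 individual tasks that can be combined into three domain specific scores". Section 7.1 lists as the co-primary executive outcome the "executive composite and domain scores derived from the NIH Examiner and b) the Stroop interference score". Section 5 (Aim 1) has a third wording: individual and composite Examiner scores, plus a Stroop task.

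**Memory.** Section 5 says the co-primary outcome includes the Arena task, names no other memory task there, and leaves additional measures as secondary. Section 6.6.2b says of the Arena task: "The dependent variable will be this navigational performance composite". Section 7.1 lists the "delayed recall scores and composite from the Arena and b) delayed recall score from the AVLT".

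**Decision rule.** Section 7.3 makes post-hoc analyses depend on significance but gives no alpha, sidedness, adjustment or any/all rule for Aim 1. The only numeric threshold in the documents, a family-wise 0.05 in section 6.8, concerns resting-state fMRI. The SAP, written in the past tense, specifies t-tests on change scores and uses Cohen's d to help choose measures for later trials. It names no primary variable, alpha or interval.

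**The concern.** The text that fixes the primary outcomes should give the same list wherever it appears, and every item on it should be obtainable. Here the Examiner domain scores are co-primary in one section and absent from the primary variable in another, and one memory co-primary has no source in the task description. With no success rule, a favourable result on any listed variable could be presented as a co-primary finding.

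Section 6.7.2 says the brief protocol is meant to determine potential effect sizes and feasibility. For that purpose the precision of d matters at least as much as the p-values. Without an interval, a reader cannot see how little a d from arms of 10 to 35 people pins down.

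**Working it through.** **1. Count the Aim 1 variables in section 7.1.**
- Executive: composite (1) + domain scores (3, the number given in section 6.6.1a) + Stroop interference (1) = 5.
- Memory: Arena delayed recall (at least 1) + Arena composite (1) + AVLT delayed recall (1) = at least 3.
- Total: at least 8.

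**2. Check that each can be computed.** In section 6.6.2b the Arena has eight acquisition trials, each recording path length, time to target and whether the target was found. Then "A final spatial memory probe occurs following the 8th trial", and "On the probe trial, path length and percent of time spent in each quadrant of the Arena is recorded". No delay interval or recall score is described. That leaves 8 - 1 = 7 computable variables. If delayed recall was loose wording for the probe, time in the proximal quadrant is already part of the Arena composite.

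**3. False-positive chance if any one suffices.** The plan gives no figure to reproduce. Assumptions: two-sided 0.05, no true effect, normal change scores, t-tests as in the SAP.
- Independent tests: 1 - 0.95^7 = 0.302. This is an upper bound that cannot be reached, because the scores share tasks; the fluency counts, for example, are scores "which contribute to the Executive Composite and Fluency Factor scores".
- Overlap modelled: composite = mean of the three domain scores; the domains, Stroop, Arena composite and AVLT share one common correlation. Simulation of 40,000 null trials at 35 per arm gives about 25% at correlation 0.3, 21% at 0.5 and 16% to 17% at 0.7. Results at 20 and 10 per arm are practically the same.
- All must succeed: at most 5%, and 0.3% or less in the simulations.

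**4. Across cohorts.** Section 7.3 analyses the groups separately. If Holm holds each cohort to 5%, the chance of at least one false claim is up to:
- three cohorts (MCI pooled, 10 + 10 = 20 per arm): 1 - 0.95^3 = 0.143;
- four cohorts (MCI split, 10 per arm): 1 - 0.95^4 = 0.185.

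The documents do not settle which applies.

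**5. Precision of d.** Planned numbers per arm come from sections 6.2 and 7.2.a. Intervals come from inverting the noncentral t; at d = 0 the half-width reduces to 1.96 × sqrt(2/n).

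| n per arm | Cohort | Half-width at d = 0 | 95% interval at d = 0.5 |
|---|---|---|---|
| 35 | Cognitively normal | 0.47 | 0.02 to 0.97 |
| 20 | Parkinson, or MCI pooled | 0.62 | -0.13 to 1.13 |
| 10 | Each MCI group if split | 0.88 | -0.40 to 1.38 |

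Section 7.3 says some MCI analyses will be truncated, so the last row applies only if they are run. The SAP speaks of a small N but does not give it; fewer participants would widen every interval.

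**The case against.** Much of the apparent conflict can be read away, and part of that defence stands.

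- A reader might infer that section 6.6.1a makes the composite the sole executive primary and rules Stroop out. It does not. The sentence sits in the Examiner subsection and chooses among Examiner scores. Stroop has its own dependent variable in section 6.6.1b, and sections 5 and 7.1 both place it in the Aim 1 executive outcome. The clear conflict is the composite alone against the composite plus domain scores.
- A reader might infer that section 5 makes Arena the only memory co-primary and AVLT secondary. Section 5 says the outcome includes Arena and does not mention AVLT. Likewise, section 6.6.2b names the Arena task's own variable, not the sole memory primary. The lists differ, but AVLT is not directly contradicted.
- A reader might take 21%, or the 30% under independence, as the trial's actual error rate. The documents state neither the 0.05 nor the any-one-suffices rule.
- A reader might quantify selection bias as the largest of seven d values. The SAP refers to potential cognitive measures generally, and the battery also holds the MST, CALCAP, Trail Making and Digit Symbol tests. Nothing says the largest d decides. Only the direction of the bias can be stated.
- A reader might conclude that no intervals were calculated. Silence in a three-sentence SAP does not show that.

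The pilot purpose also makes formal error control less pressing. It does not remove the point: sections 5 and 7.3 still set out hypotheses to be tested, and section 7.1 uses the co-primary label.

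**Conclusion.** The concern holds in this form. The Examiner domain scores are co-primary in section 7.1 but not part of the primary-aim variable in section 6.6.1a. Section 5 words the executive and memory outcomes differently again. The Arena delayed recall item has no source in the task as described, although a score available elsewhere in the software cannot be excluded. No alpha or any/all rule is given for Aim 1, and the SAP does not settle any of this.

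The error-rate consequence is conditional: about 21% per cohort under the stated assumptions (about 25% down to 16% to 17% over correlations 0.3 to 0.7), and no inflation if all variables must succeed. The imprecision of d depends less on assumption. At the planned sizes, half-widths near zero run from 0.47 to 0.88, so a d of 0.5 is compatible with almost no effect at 35 per arm and with harm or large benefit at 10. This should be corrected; it does not invalidate a pilot.

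**What to change.** 1. Delete the Arena delayed recall item from section 7.1, or relabel it as probe-trial quadrant time if that was meant, and bring sections 5, 6.6.1a and 7.1 to one list.
2. Because the SAP reads as written after the analysis, make the exploratory route the default. Report every Aim 1 outcome listed in section 7.1 that can be computed, label all tests exploratory, and make no significance claim for Aim 1.
3. Report d with a noncentral-t 95% interval for every cognitive measure in each cohort, say whether the MCI groups are pooled, and state that a d picked because it is large overstates the effect.
4. Only if it can be documented that outcome data had not been seen, name one co-primary per domain (Examiner composite, Arena composite) with an alpha and an any/all rule. Use Holm within each cohort if either suffices, and note that this does not control error across cohorts. Otherwise date any narrowing of the list and disclose it as post hoc, since it could be driven by results.

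The cost is wording plus intervals from data the trial collects anyway. The downside is that fewer results can be claimed as confirmatory and the effects will look less precise.
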